## 5. Amendments

This is the final protocol version subject to the approval by the relevant Ethics Committees (EC)/Institutional Review Boards (IRB). Subsequently, possible amendments will be submitted to the relevant EC/IRB before being implemented and will constitute a separate document. In case of major amendments, a new comprehensive version of the protocol may be prepared, incorporating all the minor and major amendments approved until that date.

## 6. Rationale and justification

### 6.1 Background

The reference international guidelines [1] recommend initial treatment of DVT of the lower limbs and/or PE with a direct anticoagulant (oral or parenteral) followed by a period of anticoagulation therapy with the same direct oral anticoagulant or partially overlapping it with a Vitamin K antagonist (VKA), with a preference for the former alternative.

An exception is represented by a VTE associated with an active cancer. In this case, a treatment with parenteral anticoagulant (in particular LMWH) for the whole period of 3 months is recommended.

Anticoagulation therapy is essential for at least three months in all cases. The incidence of VTE recurrence is considered to be very low when an event is triggered by surgery or another specific risk factor. In these cases, a three-month treatment is considered sufficient. In case of idiopathic (unprovoked) events, however, such period may not be sufficient due to the marked tendency of VTE to recur. In these cases, it is advisable to assess each subject's specific benefit (expected decrease in recurrences) in comparison with the risk of bleeding associated with prolonged anticoagulation, and determine the duration of anticoagulation based on this evaluation. However, pre-determined time-limited courses of therapy longer than 12 months are unusual [1]. In addition, based on the local healthcare system, not all regimens can be protracted indefinitely in all cases.

At the end of the three months – or longer, usually not more than one year – of anticoagulation, the attending physician has to decide whether and how to manage the long-term secondary prevention of recurrences, based on an assessment of the individual ratio of risks of recurrence and of bleeding. These individual estimates are often difficult to evaluate. A number of additional factors also influence the decision, including subject's predicaments and preferences, concurrent diseases and treatments, healthcare system support, and availability of potentially effective alternative treatments, such as aspirin [2] and sulodexide [3].

The choice of whether to continue at all the secondary prophylaxis and, if continued, the selection of the appropriate treatment and the relevant duration after maintenance anticoagulation, is therefore far from standardized. The practical clinical behavior may consequently be very dissimilar case to case, and practice guidelines, literature and local healthcare provisions do not help much in facing this problem.

### 6.2 Justification of the study

At the end of the recommended or practicable period of anticoagulation after a first-ever episode of VTE, the attending physician has therefore three different options:

1. continue with extended anticoagulation using a treatment of the same or other anticoagulant class (NOACs or VKAs or LMWHs) at the same dosage as in the previous period or with a lower dosage;
2. replace the anticoagulant with an alternative antithrombotic (including antithrombotic proper, antiplatelet or vasoprotective drug) with or without compression therapy;
3. interrupt any specific pharmacological treatment (with or without compression therapy).

Little is known as to which proportion of subjects is assigned to each alternative and whether this proportion is equivalent across different healthcare systems, and very little is known about the reasons guiding the physician's decision.

After the decision is taken, a number of validated data is available in the literature regarding the outcomes in subjects assigned to extended anticoagulation for up to one year, [4-6] whereas little if any information is available for subjects receiving extended anticoagulation for more than one year, or assigned to alternative long-term treatment, or who stopped the treatment.

The Fondazione Arianna promotes this international, investigators-initiated, multicenter observational study, to collect data that may possibly answer the first question, and give substantial indications concerning the second question.

## 7. Research question and objectives

### 7.1 Research question

The research question prompting this study is the decisional process that assigns subjects with previous VTE who concluded the maintenance anticoagulation, to one of the alternative options: extended anticoagulation, alternative pharmacological prophylaxis, or interruption of the pharmacological prophylaxis. The secondary research question is the estimation of the true rate of events during prolonged observation under true-to-life conditions, among subjects allocated to extended anticoagulation or to alternative prophylaxis or to no pharmacological prophylaxis.

### 7.2 Objectives

#### 7.2.1 Primary objective

The primary objective of the study is the assessment of the distribution of decisions on the modality to manage the secondary prevention of venous thromboembolism (VTE), at the end of the period of anticoagulation considered standard. This period, initiated after the index event and defined in the present protocol as maintenance anticoagulation, ranges from the end of the 3rd month to the end 12th month. The anticoagulant used for the maintenance anticoagulation may or may not be the same used in the initial acute phase of VTE management (the initial 7 days). To the effect of this study, the treatment applied during the acute phase is of no interest.

#### 7.2.2 Secondary objectives

The distribution of the reasons guiding the physician's decision indicated in § 7.2.1 is to be considered a secondary objective since, to date, there is no indication as to whether and which factor may represent an explanatory variable guiding the decision taken.

The secondary objective is the collection of data on the course of thromboembolic complications, bleeding complications and death risk, during a relatively prolonged follow-up. This information is already available in the literature for subjects who continued with anticoagulation for up to one year [4-6], whereas no solid information is available for subjects under longer treatment or who switched to an alternative antithrombotic prophylaxis or interrupted the treatment.

The period of follow-up after terminating the standard anticoagulation treatment is limited in this study to 2 years, since there is no evidence that after such period the risk of events is different from that of a matched population without a previous VTE episode. Since data on late recurrence rates are contrasting and somewhat obsolete, a DMSB is established to guide the conduct of the study (§ 11.3).

## 8. Methods

### 8.1 Study design

This is an international, no-profit, multicenter, observational, prospective study. The study encompasses two sections:

- a] a transversal section, in which the primary objective (and the related secondary objective on the reasons suggesting the primary objective) will be evaluated;
- b] a longitudinal section, in which the other secondary objectives will be evaluated.

The transversal section includes one population; the decision representing the primary endpoint, taken during the initial visit, will instead generate three sub-populations with regards to the secondary prophylaxis of VTE:

- a] subjects receiving extended anticoagulation, with the same or another substance of the same class, at the same or lower dose as used in the maintenance treatment;
- b] subjects receiving long-term antithrombotic non-anticoagulant prophylaxis;
- c] subjects not receiving any long-term pharmacological prophylaxis.

The secondary endpoints collected during the follow-up will be stratified by sub-population.

#### 8.1.1 Primary endpoint

The primary endpoint is the proportion of subjects allocated by the attending physicians at the end of the maintenance anticoagulation initiated after the index event, by free and spontaneous decision, to one of the three possible options:

- a) continue with anticoagulation, using the same substance or a substance of the same class, with the same or lower dosage ("extended anticoagulation"), with or without compression therapy;
- b) replace the anticoagulation with an alternative treatment (with or without compression therapy),
- c) interrupt any pharmacological prophylactic treatment (with or without compression therapy).

The primary endpoint will be evaluated at the first visit, that is, at the end of the maintenance anticoagulation.

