### 8.2.3 Exclusion criteria

Subjects meeting any of the following criteria will not qualify for entry into the study:

- a) subjects  $< 18$  years old at the time of consent request;
- b) subjects unable or unwilling to issue the written informed consent;
- c) subjects for whom the information relevant to the index event are incomplete or inaccessible to the Investigator;
- d) subject in whom the index event was a DVT not of the lower limbs;
- e) subjects with life expectancy of less than 2 years;
- f) subjects participating in any other clinical study, regardless of its nature;
- g) subjects considered, by the attending physician, unable to comply with the study procedures.

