### 10.2 Sample size

The study anticipates recruiting approximately 3,200 subjects, based on considerations relevant to the primary endpoint.

The primary endpoint is the decision taken by the attending physician at the end of the maintenance anticoagulation initiated after the index event. Three options are possible: continue with extended anticoagulation (regardless of individual drug and dose), replace the anticoagulation with an antithrombotic, non-anticoagulant treatment, or stop any pharmacological prophylactic treatment.

In absence of other determinants, the null hypothesis is that the distribution of subjects by option is uniform. The analysis can therefore be performed with a goodness-of-fit test with 2 degrees of freedom. The alternative hypothesis is that at least one of the three choices is selected in a greater proportion than the other two. This analysis is performed once only at the end of recruitment.

With approximately 3,200 subjects, the study has 90% power to detect with 95% confidence a deviation from the uniform distribution, in case one of the options is selected in a proportion exceeding by 10% relative or more the proportion expected from the uniform distribution (i.e., in 36.3% or more of the subjects) [7].

Given that the factor “country” (synonymous of “healthcare system”) will be a likely cofactor in the analyses, the sample should be split across the participating countries in such a way to allow a reliable representativeness also for the smaller countries. The limit was considered not less than 100 subjects per country. The anticipated contribution by country was therefore estimated as:

Country	cases
China	approximately 200
Czechia	approximately 350
Mexico	approximately 300
Poland	approximately 900
Portugal	approximately 350
Romania	approximately 250
Russia	approximately 800
Slovakia	approximately 150
Tunisia	not less than 100

Since in this study the secondary endpoints are of clinical relevance as well, it is appropriate to estimate whether the indicated sample can yield reliable information also in relation to such endpoints.

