**THE INDEX EVENT WAS ASSOCIATED WITH:**

surgery	 0-no; 1-yes
severe trauma	 0-no; 1-yes
cancer	 0-no; 1-yes
motor function impairment (paraplegia)	 0-no; 1-yes
limb immobilization in the 3 months before the event	 0-no; 1-yes
central venous catheter	 0-no; 1-yes
chronic inflammatory disease	 0-no; 1-yes
bed rest >4 days	 0-no; 1-yes
pregnancy	 0-no; 1-yes; 9-N/A
puerperium	 0-no; 1-yes; 9-N/A
obesity	 0-no; 1-yes
heart failure	 0-no; 1-yes
nephrotic syndrome	 0-no; 1-yes
thrombophilia	 0-no; 1-yes;
polycythemia/thrombocythemia	 0-no; 1-yes
antiphospholipid antibody	 0-no; 1-yes
estrogens and/or progestins	 0-no; 1-yes
atrial fibrillation	 0-no; 1-yes
inferior vena cava filter	 0-no; 1-yes
long travel (> 4 h)	 0-no; 1-yes
other (specify)	 0-no; 1-yes
other; specification	.....

The index thromboembolic event was:	 idiopathic	 secondary
(only one choice; radio-button type)		

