**Please specify whether compression therapy is prescribed:**

no:  0   yes:  1   specify mmHg recommended: |        | [text]

**Reasons for taking this decision  
(please tick all what applicable)**

No need of further treatment		0-no; 1-yes; default=no
Risk of thromboembolic recurrence		specify:  high-medium  low [HELP BOX FOR CRITERIA]
Risk of bleeding		specify:  high  medium  low [HELP BOX FOR CRITERIA]
Major bleeding event during treatment		
Difficulty to maintain the proper INR		
Consideration of patient's age		
Presence of Post Thrombotic Syndrome		
Presence of thrombophilia		specify: _____ [text]
Familiarity for venous thromboembolism		
Implantation of vena cava filter		
Presence of pulmonary hypertension		
Worsening of general conditions (not cancer)		
Worsening/onset of renal insufficiency		
Tendency to falls		
Presence of cancer		
Onset of contraindications		specify: _____ [text]
Decision by the patient's family doctor		
Choice of the patient		
Cost for the patient		
Positive D-dimer value		specify value:  _ _  D-DU  FEU 
Negative D-dimer value		specify value:  _ _  D-DU  FEU 
[if D-dimer value specified, one of the units MUST be specified]		
Patient involved in choosing the prescribed therapy		0-no; 1-yes; default=no
Patient's GP involved in choosing the prescribed therapy		0-no; 1-yes; default=no
Planned duration of this therapy:  not applicable [if decision=2, only possible choice]  not defined  to be evaluated  defined; specify:  _ _ _    months  years		

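### Subjects with another indication for anticoagulation may be enrolled and counted as extended VTE prophylaxis, and the closed reason list cannot record why

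*Combined protocol and SAP*

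**What the plan says.** **Objective and endpoint.** Section 7.2.1 sets the primary objective as the "assessment of the distribution of decisions on the modality to manage the secondary prevention of venous thromboembolism (VTE"). Section 8.1.1 measures it as the proportion of subjects allocated "by free and spontaneous decision, to one of the three possible options". Section 10.2 describes the first option as "continue with extended anticoagulation (regardless of individual drug and dose"); it sets no condition on the indication for the drug.

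**Eligibility.** Section 8.2.3 opens with "Subjects meeting any of the following criteria will not qualify for entry into the study" and lists items a to g. None concerns another indication for anticoagulation, and neither does any inclusion criterion in section 8.2.2.

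**CRF (Appendix IV).**
- The entry "atrial fibrillation" appears once, among factors associated with the index event.
- The concurrent-diseases list does not name it. That list ends with an Other diseases tick box that has no specification field.
- The block headed "Reasons for taking this decision" has 21 tick-box reasons. None is another indication for anticoagulation, and there is no open reason. Its two text fields for specifying a reason belong to thrombophilia and to contraindications.

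**Analysis.** Section 10.3 analyses the total sample, apart from major deviations named by the Steering Committee. Sections 10.4.2 and 10.4.3 plan no flag or sensitivity analysis for these subjects.

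**The concern.** For a subject who needs an anticoagulant for another disease, continuing it says little about how the physician would have managed VTE prevention alone. The plan does not separate this subject from one for whom all three options were open. Three results are affected.

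1. **Decision shares.** The extended-anticoagulation share mixes VTE decisions with decisions settled by another disease. More recruitment does not remove this. If the mix differs between countries, it also enters the country comparison foreseen in sections 10.2 and 10.4.2.
2. **Reasons.** Section 7.2.2 makes the reasons an objective because the explanatory factors are unknown. A closed list that omits a decisive reason leaves the investigator to tick something unrelated or nothing.
3. **Follow-up.** The thrombotic complications on the follow-up form include TIA, ischemic stroke and cardiac death. Some of these events, and some bleeds and deaths, may belong to the other disease and may be unevenly spread across the three sub-populations.

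The protocol recognises the issue after baseline: section 8.3.1 ends follow-up when an intervention requires prolonged anticoagulation. There is no counterpart at the enrollment visit.

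**Working it through.** **Inputs from section 10.2.** N = 3,200 ("With approximately 3,200 subjects"); "the null hypothesis is that the distribution of subjects by option is uniform"; goodness-of-fit test with 2 degrees of freedom; alpha 0.05; 90% power when one option reaches 36.3%.

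**The plan's own figure.** With shares 0.363, 0.3185 and 0.3185:

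- w² = 3 × [(0.363 − 0.3333)² + 2 × (0.3185 − 0.3333)²] = 0.00396, so w = 0.0629.
- Noncentrality = 3,200 × 0.00396 = 12.67.
- Power = 90.05%, and 90% power needs N = 3,196.

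The stated 90% reproduces. The point disputes no figure in the plan.

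**Effect on the extended share.** Let f be the share of subjects bound to anticoagulation by another indication, and p the share choosing it among the rest.

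- Observed share = f + (1 − f)p.
- Increase over p = f(1 − p).

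The documents give no value for f, so it is an assumption shown over a range.

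*Case p = 1/3 (others split evenly).* Observed share = 1/3 + 2f/3. The departure from uniformity is w² = 2f², so the noncentrality is 6,400f².

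| f | Subjects of 3,200 | Observed share | Probability that the test rejects |
|---|---|---|---|
| 2% | 64 | 34.7% | 28% |
| 3% | 96 | 35.3% | 57% |
| 5% | 160 | 36.7% | 96% |

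Setting 1/3 + 2f/3 = 0.363 gives f = 4.45%, about 142 subjects. On this assumption alone, the full deviation that the study is sized to detect would appear with no preference among the other subjects.

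*Case p = 50%.* Increase = 0.5f.

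| f | Increase (points) |
|---|---|
| 2% | 1.0 |
| 5% | 2.5 |
| 10% | 5.0 |

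For scale, the 95% confidence half-width at 50% is 1.96 × √(0.25/3,200) = 1.7 points. The increase is below this at f = 2% and above it at f = 5%.

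**Can these subjects be found afterwards?** Three CRF entries help, each incompletely:

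- The atrial fibrillation box asks about association with the index event, not about a current indication.
- The Other diseases box does not say which disease.
- Antiarrhythmic agents and digitalis, in the medication list, are indirect clues.

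None of them records that another indication decided the treatment. After the end-of-study form a case is closed to users and can be re-opened only on an endorsed request, so later recovery is laborious.

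**The case against.** **Such subjects may not enter.** Section 8.2.2 requires that the subject is to be re-evaluated for the next treatment, and section 8.3.1 defines the baseline visit as the one where continuation of prophylaxis must be decided. A centre could read this as leaving out a subject with no open decision. A reader might infer from the missing exclusion that these subjects are enrolled; the documents show only that they may be. This part stands, but it also means that centres may act differently.

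**A constrained decision is still a decision.** Sections 6.1 and 8.3.1 describe a choice based on personal judgment and local procedures, with concurrent diseases among its influences. On that reading, atrial fibrillation is one more determinant of usual practice, and counting the subject is not an error. This stands for the total-sample result. It does not excuse a reason list that cannot show the determinant.

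**The CRF is not blind.** A reader might infer that unlinked atrial fibrillation leaves no trace. The Other diseases box and the drug items contradict that; identification is partial.

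**The follow-up effect is limited.** A reader might infer that the other disease adds events to the extended group only. Nothing in the documents says that every such subject continues an anticoagulant. Thrombotic events are also recorded by type, so venous and arterial events can be separated; bleeding and death cannot be separated in this way.

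**The size is hypothetical, and models are available.** f is assumed, and section 10.1 calls the analyses exploratory, so crossing 36.3% has limited weight. Sections 10.4.2 and 10.4.3 allow regression on prognostic factors and predictors, but these models are optional and can use only what was recorded.

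**Conclusion.** The point holds as a gap in eligibility wording and data capture. Another indication for anticoagulation is not addressed at entry, is only partly identifiable on the CRF, and cannot be entered as a reason. The effect on the reasons endpoint follows directly from the form for any such subject enrolled.

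The effect on the decision shares is conditional. It is f(1 − p): 1.3 to 3.3 points at p = 1/3 for f of 2 to 5%, and 1.0 to 5.0 points at p = 50% for f of 2 to 10%. This rests on an assumed f and on all such subjects continuing an anticoagulant. If only a share q of them do, the effect is f(q − p), which is smaller. A reader might infer that the primary result is inflated by a known amount, or that rejection of uniformity would be spurious. The documents support neither, because they give no prevalence and the even split among the remaining subjects is only the null hypothesis.

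Nor do the documents require these subjects to be removed from the main result; section 10.3 defines that as the total sample. The change is worth making because the information is cheap to collect at baseline and hard to recover later.

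**What to change.** 1. In the concurrent-diseases section of the baseline CRF, add a yes/no item: *current indication for anticoagulation other than VTE*.
2. In the reason list, add *other indication for anticoagulation* and *other, specify*.
3. Keep the total sample of section 10.3 as the main analysis.
4. In sections 10.4.2 and 10.4.3, add one sentence each that pre-specifies a sensitivity analysis of decision shares, reasons and event rates without subjects who have another indication.

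The cost is three CRF fields, a little more analysis, and a smaller denominator in the sensitivity analysis only: 3,200 × (1 − f), which is 3,136 at f = 2% and 2,880 at f = 10%. Enrollment and care are unchanged.

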Study Procedures	
Enrollment and baseline visit:
 
 
1. the physician will assess the inclusion/exclusion criteria for entering the study and obtain the informed consent to confer the study data;
 
2. after obtaining the consent, the attending physician will record the diagnostic and prognostic information required in the CRF and inform the promoter of the recruitment of the patient;
 
3. the attending physician, based exclusively on the personal judgment and in accordance with the local procedures, will decide whether to continue with anticoagulation (NOACs or VKAs or LMWHs); or to switch to a long-term antithrombotic prophylaxis; or permanently discontinue the pharmacological prophylaxis. This decision generates three sub-populations with regards to the secondary prophylaxis of VTE: 
 
a] subjects receiving extended anticoagulation, with the same or another substance of the same class, at the same or lower dose as used in the maintenance treatment;
 
b] subjects receiving long-term antithrombotic non-anticoagulant prophylaxis;
 
c] subjects not receiving any long-term pharmacological prophylaxis.
 
 
 
4. the attending physician will record in the CRF the reasons guiding the decision taken;
 
5. the physician will instruct the subject on the procedures of the follow-up that should be the normal procedures in use at the Center, will provide a contact
 

	
reference and will obtain a contact reference.
 
Follow-up visits
 
The follow-up will be articulated as normally performed at the Center. The common follow-up procedures include a telephone contact every 3/6 months (4/8 in two years) and a direct interview at the center at least once a year (two in two years).
 
At each follow-up contact, by telephone or personal, information will be collected on:
 
 
survival at the time of contact;
 
hospitalizations occurred after the previous contact;
 
events of thromboembolic complication;
 
events of bleeding complication;
 
changes in the antithrombotic/anticoagulant therapy, if any was prescribed, including the institution of an antithrombotic/anticoagulant therapy if none had been prescribed;
 
other events that prevent the continuation of the planned follow-up.
 

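### Extended anticoagulation, a primary-endpoint category, is defined in conflicting ways and leaves some decisions without a group; separately, the CRF date check is shorter than the eligibility window

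*Combined protocol and SAP*

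**What the plan says.** **Decision categories.** The primary endpoint (section 8.1.1) is the share of subjects assigned to each of three options. Option a) is to "continue with anticoagulation, using the same substance or a substance of the same class, with the same or lower dosage"; option b) is to "replace the anticoagulation with an alternative treatment (with or without compression therapy"; option c) is no drug prophylaxis. The sub-population lists in the synopsis (Study Procedures) and section 8.1 describe the first group as treated "with the same or another substance of the same class, at the same or lower dose as used in the maintenance treatment" and the second as "subjects receiving long-term antithrombotic non-anticoagulant prophylaxis".

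Other places are wider. The synopsis sentence that introduces the list says the physician "will decide whether to continue with anticoagulation (NOACs or VKAs or LMWHs". Section 6.2 expressly admits a move to a different anticoagulant class, still at an unchanged or reduced dosage. Section 10.2 gives the first option as "continue with extended anticoagulation (regardless of individual drug and dose" and the second as "replace the anticoagulation with an antithrombotic, non-anticoagulant treatment".

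The same groups are used after baseline: "The secondary endpoints collected during the follow-up will be stratified by sub-population" (section 8.1).

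**Entry window.** Section 8.2.1 sets 3 and 12 months as the limits of prior anticoagulation. Section 8.2.2 calls 3 to 12 months usual. Section 8.3.1 allows the enrolment visit up to one month after anticoagulation has ended. The index-episode form in Appendix IV requires the diagnosis to lie between 90 and 360 days ahead of consent.

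**The concern.** A three-way proportion needs categories that do not overlap and leave nobody out. Here the rule that generates the groups is narrower than the rule behind the sample size, and the second group cannot take the remainder because it is confined to non-anticoagulants. A subject whose anticoagulant dose is raised, or who perhaps moves from one anticoagulant class to another, is counted in the first group by one section and by none in another. Two analysts following different sections would report different primary proportions with their confidence intervals (section 10.4.2), and would put different people in the strata for recurrence, bleeding and death.

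The date check is a separate matter with a different consequence. A misplaced category can be recoded later. A subject refused by an entry check leaves no data to recode.

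**Working it through.** **1. The plan's own figure.** Section 10.2 claims 90% power with 3,200 subjects when one option has 36.3%. Take p = (0.363, 0.3185, 0.3185) against 1/3 each.
- w² = Σ(p − 1/3)²/(1/3) = 0.00396; λ = 3,200 × 0.00396 = 12.67.
- With 2 degrees of freedom and critical value 5.99, power = 0.900.

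The figure reproduces. The definitional problem does not touch the sample-size arithmetic.

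**2. Where each decision falls.** For the switch columns, assume the dose condition is otherwise met.

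| Text | Dose increase | Class switch, if class = VKA / NOAC / LMWH | Class switch, if class = all anticoagulants |
|---|---|---|---|
| Synopsis list, section 8.1 | no group | no group | first group |
| Section 8.1.1 | no group, unless read into b) | no group, or b) if an alternative treatment may be an anticoagulant | first group |
| Section 6.2 | no group | first group | first group |
| Section 10.2 | first group | first group | first group |

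The dose-increase conflict holds under either meaning of class. The class-switch conflict depends on the narrower meaning, which section 6.2 and the drug-class windows of Appendix IV both use.

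**3. Effect on the reported share.** The documents give no rate of switches or dose increases, so the rate is an assumption. Section 10.3 analyses the total sample, so keep the denominator at 3,200. Each 1% of subjects (32) coded differently then moves the extended share by 1 point. At 36.3% the 95% half-width is 1.96 × √(0.363 × 0.637 / 3,200) = 1.67 points. The shift would exceed it only above 1.67% of subjects (0.0167 × 3,200 = about 53).

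**4. Does power fall?** Suppose, contrary to section 10.3, that a share s of all subjects is dropped from the first group. Then n = 3,200(1 − s), and the proportions are rescaled by 1/(1 − s).

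| s | Power, first option at 36.3% | Power, second or third option at 36.3% |
|---|---|---|
| 0 | 90% | 90% |
| 1% | 70% | 96.0% |
| 2% | 41% | 99.0% |
| 3% | 17% | 99.9% |
| 5% | 7% | >99.9% |

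The direction depends on which option is largest, and the plan does not say which it expects.

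**5. Date window.** Counted in calendar days from diagnosis:
- 12 months = 365 to 366 days, which is 5 to 6 past the limit of 360.
- 12 months plus one month = 365 + 28 to 366 + 31 = 393 to 397 days, which is 33 to 37 past it.
- With a full one-month lag, anticoagulation must have ended by day 360 − 31 = 329 to 360 − 28 = 332 to pass.
- The lower limit of 90 days agrees with 3 months (89 to 92 days).

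**The case against.** The best defence is that the intent is visible. The synopsis lead-in, section 6.2 (on class) and section 10.2 all point to a split between anticoagulant, non-anticoagulant and nothing. The synopsis rationale uses another class for the non-anticoagulant option. The CRF collects the new treatment in two boxes along the same line: `replaced_1` (VKA, LMWH, NOAC, other) and `replaced_2` (aspirin, sulodexide, other). Drug and dose are recorded. All of this stands, and it makes the problem recoverable. It does not supply the mapping: the operative lists still say something narrower, and the options of the CRF decision field are not visible in the available text, so one cannot tell whether the database already settles it. That invisibility is not itself a fault in the plan.

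A reader might infer from step 4 that the study loses power. The documents do not support this. Section 10.3 analyses the total sample and excludes only serious deviations named by the Steering Committee; a subject with a recorded decision and drug is not missing data. The sign of the effect also reverses with the largest option, and section 10.1 declares the analyses exploratory.

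On dates, 360 days may simply be twelve 30-day months, and the one-month lag is a logistic allowance. That explains the 5 to 6 days but not the 33 to 37. Whether the check blocks entry is not stated. It is worded as a requirement, like the age limit, while some other checks only warn or ask for confirmation; yet it carries no stop instruction like that on the consent field. A reader might also count the 12 months from the end of the 7-day acute phase and reach 400 to 404 days. This is weakly supported: section 7.2.1 starts the period after the index event, and section 8.2.1 limits anticoagulant treatment without setting the acute phase aside.

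**Conclusion.** Both inconsistencies are in the text as written; severity is minor to moderate.

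(1) The categories of the primary endpoint are not exhaustive in the synopsis list and section 8.1, and they differ from sections 6.2 and 10.2. For dose increases this needs no assumption; for class switches it assumes that class means VKA, NOAC or LMWH. The effect is on the reported proportions and on membership of the follow-up strata. Its size is unknown. It is fully recoverable from recorded data, provided the mapping is fixed before the decision distribution is analysed.

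(2) The CRF date limit is 5 to 6 days short of 12 months and 33 to 37 days short of the latest enrolment that sections 8.2.1 and 8.3.1 together allow. Harm depends on the check being enforced. Neither enforcement nor the number of subjects affected can be established from the documents.

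**What to change.** (1) Use one mutually exclusive, exhaustive data classification in the synopsis, sections 6.2, 8.1, 8.1.1 and 10.2. The section 10.2 wording would serve: any anticoagulant whatever the drug and dose; non-anticoagulant prophylaxis only; no drug. This is a rule for coding decisions already taken, not for taking them. Write down the mapping from CRF fields to categories, including the free-text other entries, before the decision distribution is analysed. Report class switches and dose increases as sub-rows.

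(2) Reconcile the Appendix IV date check with sections 7.2.1, 8.2.1, 8.2.2 and 8.3.1 so that it accepts every subject the eligibility text accepts. If both the 12-month limit and the one-month allowance stand, that is about 397 days from diagnosis. State whether the 12-month limit is firm (8.2.1) or usual (8.2.2), and check recorded treatment duration separately.

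The cost is wording in five places, one mapping table and one edit-check value. No new data are needed: section 8.3.2 already collects type, dosage and duration for the maintenance treatment, and type, dosage and planned duration for the new one.
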